9.3.7. Length of Treatment

The duration of each prescription will be estimated from the days' supply, if available or will be calculated directly as the total prescription quantity divided by daily number of pills recommended in the dosing instructions. However, because domperidone may be used as needed (i.e., pro re nata [PRN]), the number of days supplied may not be a reliable measure for the actual length of treatment. Therefore, compliance with the label will be estimated with and without a requirement that the days' supply will be no more than 7 days.

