7.2. Background

In 2011, the EU Pharmacovigilance Working Party (PhVWP) recommended that the product information for domperidone-containing medicines should be updated to reflect the risk of adverse cardiac effects of domperidone including QT prolongation, arrhythmias, and sudden cardiac death, and that domperidone should be used with caution in patients with certain heart conditions, including heart failure, a previous heart attack, angina (chest pains), and heart rhythm disorders. In response to this recommendation, the SmPC was updated in 2012 to include QT prolongation as an adverse drug reaction (ADR).

In March 2013, the EMA PRAC initiated a review of domperidone-containing medicines at the request of the Federal Agency for Medicines and Health Products (FAMHP), under Article 31 of Directive 2001/83/EC over concerns about cardiac adverse effects of domperidone. Subsequently, PRAC recommended that the product label (Summary of Product Characteristics/SmPC and Patient Information Leaflet/PIL) of domperidone-containing medicines should be updated to strengthen the information regarding cardiac risks. In addition, PRAC raised concerns that there may be off-label use of domperidone for the stimulation of lactation in breastfeeding women, for the treatment of

gastro-oesophageal reflux disease (GERD), for the treatment of diabetic and non-diabetic gastroparesis, and for the treatment of symptoms of postural hypotension in Parkinson's patients. More recently the EMA asked that IBS be included in the present study as an off-label indication.

The recommended changes following conclusion of the Article 31 referral included the following:

- restriction of the indication to nausea and vomiting;
- limitation of duration of use to 7 days;
- reduction of the maximum daily dose to 10 mg TID for adults and adolescents (12 years of age and older and weighing 35 kg or more);
- reduction of the maximum daily dose to 0.25 mg/kg TID for neonates, infants, children (less than 12 years of age), and adolescents weighing less than 35 kg;
- contraindication of the combination with other drugs that increase the cardiac risks by themselves or increase the plasma level of domperidone; and
- contraindication in patients with moderate or severe hepatic impairment or certain cardiac conditions.

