8.1. Primary Objectives

To describe the prescribing patterns before and after the changes to the domperidone label and distribution of a DHPC and estimate and compare the overall proportion of domperidone prescriptions before and after implementation of the risk minimisation measures regarding the following measures:

- Composite endpoint consisting of the following components:
 - Maximum daily dose;
 - Duration of use (>7 days);
 - Concomitant medications that prolong the QT-interval or are potent or strong CYP3A4 inhibitors;
 - Prescribing to patients with contraindicated conditions, e.g., moderate or severe liver disease, underlying cardiac diseases; and
 - Prescribing for off-label indications

Domperidone is used as needed, therefore the duration of use may not be the same as the number of days for which domperidone is supplied. As a result, duration of use will be assessed under the following 2 scenarios, which will be likely to bracket the actual (but unknown) situation:

- 1. Domperidone is used only for as little as 1 dose after it is prescribed, and
- 2. Domperidone is used for the entire number of days supplied.

This is intended to bracket the plausible values for duration of use

Primary test statistic: In each country studied, the change in the proportion of all prescriptions that comply with the label based on the above composite endpoint during the 12 months before the label change versus the 12 months after the label change is the primary statistic to be evaluated as a measure of the effectiveness of the label change in that country. The statistic will be evaluated as a risk ratio, i.e., as the ratio of the proportion of prescriptions that met all conditions in the composite endpoint between 1 April 2013 and 31 March 2014 and the proportion of prescriptions that met all conditions of prescriptions that met all conditions in the composite endpoint between 1 October 2014 and 30 September 2015. The point estimate and 95% confidence interval for the above risk ratio will be reported. There are several versions of the composite endpoint are implemented in the databases and the risk ratio (point estimate and 95% confidence interval) will be reported for each. Note that the term "risk ratio" is being used in the sense of a ratio of probabilities (the probability of a prescription being consistent with the new label).

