9.3.2. Indication

Indication will be estimated from the diagnoses recorded in the time period preceding each domperidone prescription:

- The indication for the prescription will be defined as nausea/vomiting if the subject has a recorded diagnosis classified as nausea or as vomiting, on the day of the prescription or in the preceding 7 days.
- For those prescriptions whose indication is not defined as nausea/vomiting, the indication will be defined as off-label if the subject has, in the 2 months up to and

including the date of domperidone prescription, a diagnosis classified as one of the following:

- o GERD;
- Abdominal bloating, gastric dysmotility, delayed gastric emptying;
- o IBS;
- Suppressed lactation, failed lactation, lactation not established, decreased lactation, lactation problem; or
- Orthostatic hypotension and a diagnosis of Parkinson's disease.
- For those prescriptions not classified as above, the indication will be classified as unknown.

For a list of the diagnostic terms and codes that will be used to identify the above conditions, see Annex 6.

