9.3.6. A Composite Endpoint -All Label Requirements

Each prescription will be classified according to whether it appears to violate at least 1 of the above specifications, i.e., has a presumed indication that is off-label, has a dose that is above 30 mg/day (for ages \geq 12 years) or above 0.75 mg/kg/day (for ages <12 years), is written for a patient with a contraindicated condition, or appears to be prescribed concurrently with a medication contraindicated for concurrent use.

To accommodate the 2 areas of uncertainty described above (1] duration of domperidone use and 2] domperidone prescriptions for which the indication is unknown), the above classification will be done in the following 4 ways to reflect the possible combinations of:

- With consideration of days' supply being more than 7 days;
- Without consideration of days' supply being more than 7 days;
- With classifying subjects with an unknown indication as having an off-label indication; and
- Without classifying subjects with an unknown indication as having an off-label indication

This is described in more detail in Section 9.7.

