 - Prescription for nausea and vomiting but no recent diagnosis of GERD, gastroparesis, IBS, symptoms of postural hypotension in Parkinson patients, or as an aid to lactation. Unknown indication will be assumed to be off-label (This differs from #1 above);
 - b. Dose no higher than recommended;
 - c. No prescription to patients with certain cardiac and hepatic conditions; and
 - d. No co-prescription with CYP3A4 inhibitors or QT-prolonging drugs (This considers such contraindicated co-medications only when they were prescribed ≤ the date of the domperidone prescription)
- 3. Unknown indication assumed to be nausea and vomiting, duration assumed to be the days' supply (an intermediate scenario) meets the following conditions:
 - Prescription for nausea and vomiting or for unknown indication but no recent diagnosis of GERD, gastroparesis, IBS, symptoms of postural hypotension in Parkinson patients, or as an aid to lactation (This is the same as in #1 above);
 - b. Duration (days' supply) ≤7 (This differs from #1 above and from #2 above, which don't examine days' supply)
 - c. Dose no higher than recommended;
 - d. No prescription to patients with certain cardiac and hepatic conditions; and

- e. No co-prescription with CYP3A4 inhibitors or QT-prolonging drugs. (Considers such contraindicated co-medications when prescribed ≤ the date of the domperidone prescription or prescribed within the days potentially covered by the domperidone prescription).
- 4. Unknown indication assumed to be an off-label indication, duration assumed to be the days' supply (most pessimistic scenario)
 - Prescription for nausea and vomiting but no recent diagnosis of GERD, gastroparesis, IBS, symptoms of postural hypotension in Parkinson patients or as an aid to lactation; Unknown indication assumed to be off-label (This differs from #1 above)
 - b. Duration (days' supply) ≤7 (This differs from #1 above and from #2 above, which don't examine days' supply.)
 - c. Dose no higher than recommended;
 - d. No prescription to patients with certain cardiac and hepatic conditions; and
 - e. No co-prescription with CYP3A4 inhibitors or QT-prolonging drugs. (Considers such contraindicated co-medications when prescribed ≤ the date of the domperidone prescription or prescribed within the days potentially covered by the domperidone prescription).

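### Duration is tested one prescription at a time, so repeat short prescriptions always pass it; the days-supplied scenario is not an upper limit, and the duration component and composite version 3 can improve without shorter treatment

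*Protocol*

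**What the plan says.** Section 7.2 lists the measure under evaluation as "limitation of duration of use to 7 days", a limit on use rather than on the size of one prescription.

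The protocol turns this into a test on single prescriptions:

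- Section 9.3.6 sets the unit: "Each prescription will be classified according to whether it appears to violate at least 1 of the above specifications".
- Section 9.3.7 sets the measurement: "The duration of each prescription will be estimated from the days" of supply or, where that is not available, from the quantity divided by the daily number of pills.
- Section 9.7 sets the criterion. The duration line of versions 3 and 4 contains "supply) ≤7 (This differs from #1 above and from #2 above". Versions 1 and 2 do not look at days' supply. Version 4 is described as the most pessimistic of the four.

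Section 8.1 gives two duration scenarios: as little as one dose, or "Domperidone is used for the entire number of days supplied". It adds: "This is intended to bracket the plausible values for duration of use". Section 9.3.5 repeats the two scenarios and the expectation that they bracket the truth.

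Patients are followed from an index date (Section 9.2.1) and all eligible prescriptions are analysed (Section 9.5). No section links one prescription to the next.

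**The concern.** The two scenarios deal with one uncertainty only: an as-needed drug may be used for fewer days than were supplied. Repeat prescribing works the other way, because continuous use can outlast any one supply. For a patient with repeats, the days-supplied scenario can understate duration, so the bracket has no valid upper end.

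This bears on the question the study has to answer. Issuing smaller quantities more often is a foreseeable response to a 7-day limit. It replaces one failing record with several passing ones and enlarges the denominator with passes. A rise in the duration component or in version 3 could then reflect smaller prescriptions, shorter treatment or both, and the planned analysis could not separate them. The error would favour concluding that the risk minimisation measures worked.

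**Working it through.** The protocol has no figure of its own on this point to reproduce: it gives no share of long prescriptions, no repeat rate and no splitting rate. The mix below is assumed. Ratios are post over pre, as in Section 9.5.

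**Step 1, one patient.** Treatment lasts 28 days without a break.

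- One 28-day prescription: 28 > 7, so 0 of 1 passes the duration test.
- Four consecutive 7-day prescriptions: each is 7 or less, so 4 of 4 pass.

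**Step 2, duration component and version 3.** Assume 60 short prescriptions (7 days or less) and 40 28-day prescriptions before the change, with all other components met. Afterwards patients and treatment days are the same, but a fraction f of the long prescriptions is written as four 7-day ones.

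Compliance after = (60 + 160f) / (100 + 120f). Compliance before = 60/100 = 60%.

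| f | Passing / total | Compliance | Ratio | Ratio by episode |
|---|---|---|---|---|
| 0.25 | 100/130 | 76.9% | 1.28 | 1.00 |
| 0.50 | 140/160 | 87.5% | 1.46 | 1.00 |

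By episode, 60 of 100 courses last 7 days or less in both periods.

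**Step 3, other mixes.** With a share L of long courses, the ratio is [(1 − L + 4Lf) / (1 + 3Lf)] / (1 − L).

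- L = 10%: 1.03 at f = 25%, 1.11 at f = 100%.
- L = 30%: 1.17 at f = 25%, 1.43 at f = 100%.
- L = 50%: 1.45 at f = 25%, 2.00 at f = 100%.
- L = 70%: 2.19 at f = 25%, 3.33 at f = 100%.

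For scale, 1.1 is the smallest ratio in Table 2 of Section 9.5, which calls smaller improvements of limited public health interest. With few long courses and little splitting the artefact stays below that; with L from 30% to 70% and f from 25% to 100% it exceeds it.

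**Step 4, version 4.** Here an unknown indication counts as off-label. Section 9.3.2 accepts nausea or vomiting only if it is recorded "on the day of the prescription or in the preceding 7 days". A diagnosis recorded once, on day 0, covers the prescriptions of days 0 and 7. Those of days 14 and 21 become unknown and fail, so two of four pass. A diagnosis recorded once, before day 0, covers only the first.

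- f = 0.50, two of four: (60 + 40)/160 = 62.5%, ratio 1.04.
- f = 0.25, two of four: (60 + 20)/130 = 61.5%, ratio 1.03.
- f = 0.50, one of four: (60 + 20)/160 = 50%, ratio 0.83.

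Version 3 escapes this because an unknown indication passes, provided no listed off-label diagnosis falls in the 2 months up to the prescription.

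**Step 5, constant splitting.** If half of the long courses were split in both periods, per-prescription compliance would be 87.5% in both: the ratio is 1.00, but the level is overstated against 60% by episode. A false gain needs a change in splitting between the periods.

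**The case against.** The strongest case on the other side has five parts.

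- **The unit is deliberate.** The objectives in Sections 8.1 and 8.2 concern the proportion of prescriptions, and for an as-needed drug a second prescription need not mean continuous use. This stands, and it argues for adding an episode analysis rather than replacing the unit.
- **Only part of the primary result is exposed.** Versions 1 and 2 have no days' supply test, although extra prescriptions can still change their weighting. Each component is also compared separately and days supplied are tabulated, so a gain confined to duration and version 3 would be visible. This stands as a clue to interpretation, but a true shortening of treatment would look the same. Section 9.7 allows rates per 1000 treated patients where appropriate, but it does not say that duration will be reported that way, and the primary statistic is per prescription.
- **The bracket statement is hedged.** It speaks of intention and likelihood, and most pessimistic ranks four listed scenarios. That softens the wording but does not supply the missing upper end. Section 9.9.2 calls true length of treatment an important uncertainty, yet discusses as-needed use, missing days' supply and patients seen by several physicians, not repeats within one record.
- **The size is assumed.** This stands in full.
- **It could be left to the statistical analysis plan.** An added analysis could sit there, but the protocol already fixes both the unit and the criterion, so this is not a detail left open.

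A reader might infer that back-to-back 7-day prescriptions count as fully compliant even in version 4. The documents do not support that: passing is assured only for the duration component, and the 7-day diagnosis window can fail the later repeats.

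**Conclusion.** The point holds for the duration component, the days-supplied table and version 3, and in weaker form for version 4. As written, the days-supplied scenario is not an upper limit on duration for patients with repeat prescriptions, and that conclusion needs no assumed figures.

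The size does. Ratios of 1.28 and 1.46 rest on a 60/40 mix, 28-day courses split into four, no splitting before the change, unchanged treatment days and all other components met. They illustrate what the endpoint permits and do not forecast this study's result. In version 4 the half-split figure falls to 1.04 with two of four repeats qualifying, and to 0.83 with one.

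It would go too far to conclude that every version of the primary ratio is biased upward, or that the per-prescription unit must be abandoned. The defect is a missing sensitivity analysis and an over-broad statement about bracketing. Without the change, a gain in version 3 cannot be told apart from a move to smaller prescriptions.

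**What to change.** Keep the per-prescription results and make these additions:

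1. In Sections 9.3.7 and 9.7, pre-specify a sensitivity analysis that links a patient's consecutive domperidone prescriptions into episodes, with allowed gaps of 0, 7 and 14 days. Score the duration component on total episode days and count each episode once for that component.
2. Report versions 3 and 4 with the duration result of the episode applied to every prescription in it, so that indication, dose, contraindications and co-medication stay per prescription.
3. Tabulate repeat prescribing by period.
4. Reword the bracket statements (Sections 8.1 and 9.3.5) and the most-pessimistic label (Section 9.7) to say that they refer to use of a single prescription's supply and do not cover repeats.

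The cost is protocol wording and some programming on data to be extracted anyway. A gap must be chosen, hence the three values, and some separate as-needed episodes will be merged. Item 2 has its own denominator effect: in the half-split example every repeat fails, giving 60/160 = 37.5% and a ratio of 37.5/60 = 0.63. The once-per-episode component in item 1 (ratio 1.00 there) is therefore the figure to read for whether treatment length changed.

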9.4. Data Sources

Patient information on domperidone exposure and study endpoints will be obtained from existing data sources. In order to meet the study objectives, the following data sources will be considered:

Longitudinal Electronic Medical Records (EMR) Databases:

- IMS longitudinal patient databases providing systematic ongoing information from physician office-based visits on patients' consultations, diagnoses and treatment in Germany, France, Belgium, and Spain.
- CPRD: a longitudinal anonymised electronic medical records (EMRs) database containing detailed information on symptoms, diagnoses, prescriptions, investigations, and hospital referrals, as well as basic demographics. Longitudinal data are collected for a sample of over five million active patients registered with over 650 general practices throughout the United Kingdom.

These data sources and countries are subject to change depending on data availability. For additional details on the electronic databases, see Annex 5.

9.5. Study Size

The study size will vary according to country and data source. All patients available in the study population will be considered for the analysis. Preliminary estimates indicate that the suggested databases capture at least several thousands of domperidone prescriptions in each of the countries being studied.

Review of domperidone sales data for 2015 from IMS and from the CPRD indicates that the number of prescriptions in each of the databases varies by country. The lowest number of prescriptions was observed in the Belgian database, where the count was 22,000.

Table 2 shows the approximate number of prescriptions for a study with the same number of prescriptions in pre-intervention period and the post-intervention to have 90% power to detect, p<0.05 (2-sided test) risk ratios from 1.1 to 1.4 according to the risk during the pre-intervention period. Note that the "risks" are the probabilities of a prescription meeting the label requirements, so a risk ratio of 1.1 represents a 10% improvement in label compliance when comparing the post-intervention period to the pre-intervention period.

Table 2:Approximate number of Subjects Required per Group (Before Intervention, After Intervention) Under Various Scenarios				
"Risk" of complying with label before	"Risk" Ratio =	"Risk" Ratio =	"Risk" Ratio =	"Risk" Ratio =
the intervention period	1.1	1.2	1.3	1.4
10%	16,000	4,500	2,000	1,200
20%	7,200	1,800	900	500
30%	4,000	1,100	500	300
40%	2,700	700	300	200
50%	1700	500	200	100
60%	1200	300	200	100
70%	700	200	100	100
80%	400	100	100	100

Thus, if compliance with the new label requirements as low as 10% in the pre-intervention period, the study will have \geq 90% power to detect even a risk ratio of 1.1 (a 10% improvement), and smaller improvements would be of limited public health interest. If compliance with the new label is higher than 10% in the pre-intervention period, the study will have \geq 90% power to detect smaller improvements in compliance with the new label. All domperidone prescriptions that are captured during the study period and meet the inclusion criteria will be included in data analysis.

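### Table 2 is stated for 90% power at two-sided p<0.05, but 24 of its 30 feasible cells fall short of that and two further cells imply compliance above 100%

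*Protocol*

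**What the plan says.** Protocol section 9.5 describes "a study with the same number of prescriptions in pre-intervention period and the post-intervention" and says that Table 2 gives the size needed for "90% power to detect, p<0.05 (2-sided test) risk ratios from 1.1 to 1.4". The title of the table is "Approximate number of Subjects Required per Group (Before Intervention, After Intervention) Under Various Scenarios". The section defines the risks as probabilities that a prescription meets the label, and adds that "a risk ratio of 1.1 represents a 10% improvement in label compliance when comparing the post-intervention period to the pre-intervention period".

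Rows run from 10% to 80% baseline compliance and columns from ratio 1.1 to 1.4. The 10% row prints 16,000 / 4,500 / 2,000 / 1,200. The 80% row prints 400 / 100 / 100 / 100. The same section gives 22,000 prescriptions in the Belgian database as the lowest country count, from 2015 data. It concludes that, at 10% baseline, the study has at least "90% power to detect even a risk ratio of 1.1 (a 10% improvement").

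The amendment table in section 5 records that this material was added after the EMA asked for a sample size calculation. Section 8.1 makes the risk ratio, with a 95% confidence interval, the primary statistic in each country.

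**The concern.** Section 9.5 fixes every input to the calculation: test, sidedness, power, allocation, baseline and ratio. Each cell can therefore be checked directly. If the sizes are too small for the stated test, the answer given to the regulator overstates how much spare capacity the smallest database has. Because the primary statistic is evaluated country by country, the Belgian margin is the one that matters. An 80% baseline with a ratio of 1.3 or 1.4 also cannot occur when the quantity is a probability.

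**Working it through.** **Inputs (all from section 9.5).** Two-sided alpha 0.05, power 90%, equal numbers per period, p2 = p1 × ratio. Normal quantiles: 1.960 (two-sided 5%), 1.645 (one-sided 5%), 1.2816 (90% power).

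**Formula.** With p̄ = (p1 + p2)/2,

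n per period = [z_α √(2p̄(1−p̄)) + 1.2816 √(p1(1−p1) + p2(1−p2))]² / (p2 − p1)².

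**First cell: 10% baseline, ratio 1.1.** p1 = 0.10, p2 = 0.11, p̄ = 0.105.
- √(2 × 0.105 × 0.895) = 0.43353 and √(0.09 + 0.0979) = 0.43347.
- Two-sided: (1.960 × 0.43353 + 1.2816 × 0.43347)² / 0.01² = 19,747. The table prints 16,000, which is 3,747 (19%) short.
- One-sided 5%: replacing 1.960 by 1.645 gives 16,094.
- Two-sided power at 16,000: Φ[(0.01 × √16,000 − 1.960 × 0.43353)/0.43347] = Φ(0.958) = 83.1%.

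**The ratio 1.1 column.**

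| Baseline | Printed | Two-sided, 90% | One-sided 5%, 90% | Two-sided power at printed size |
|---|---|---|---|---|
| 10% | 16,000 | 19,747 | 16,094 | 83.1% |
| 20% | 7,200 | 8,714 | 7,102 | 83.8% |
| 30% | 4,000 | 5,037 | 4,105 | 82.3% |
| 40% | 2,700 | 3,198 | 2,606 | 84.6% |
| 50% | 1,700 | 2,095 | 1,707 | 83.2% |
| 60% | 1,200 | 1,359 | 1,108 | 86.1% |
| 70% | 700 | 834 | 679 | 84.4% |
| 80% | 400 | 440 | 358 | 87.1% |

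**Does another formula explain it?** For the first cell, two-sided unpooled, log-ratio and arcsine versions give 19,739 to 19,769, and a continuity correction gives 19,947. None comes near 16,000.

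**All feasible cells.** In 24 of 30, two-sided power at the printed size is below 90%; 23 of these are more than 3% too small. The six that reach 90% are small cells at 60% to 80% baseline printed as 100 or 200.

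**Impossible cells.** 0.80 × 1.3 = 1.04 and 0.80 × 1.4 = 1.12. Both print 100 per group.

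**Effect on the stated conclusion (10% baseline, ratio 1.1).** Take 22,000 as the number of eligible, independent prescriptions in each period. Power = Φ[(0.01 × √22,000 − 0.8497)/0.43347] = Φ(1.46) = 92.8%.
- Margin as printed: 22,000/16,000 = 1.38. Margin as corrected: 22,000/19,747 = 1.11.
- Section 9.2.1 requires 180 days of prior history, but the documents give no rate of loss to this rule. As an assumed range:

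| Assumed loss | Eligible per period | Power |
|---|---|---|
| 0% | 22,000 | 92.8% |
| 10% | 19,800 | 90.1% |
| 20% | 17,600 | 86.4% |
| 30% | 15,400 | 81.7% |

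The printed requirement of 16,000 would pass the 20% row; the corrected requirement does not.

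**The case against.** The strongest reply is that nothing in the study depends on the table. The data are retrospective, section 9.5 includes every eligible prescription, section 9.7 calls the analysis descriptive, and Annex 2 says that no formal hypothesis is tested. Correcting the table alters no sample, estimate or interval. That stands, and it limits the weight of the point.

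The text and the table title also call the figures approximate. Rounding accounts for some scatter, but not for a 19% gap in the key cell or for a shortfall in 24 of 30 cells.

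Two stronger readings are tempting, and the documents support neither.
- A reader might infer that the table was calculated for a one-sided test. The printed sizes lie close to one-sided 5% values, so this is a likely explanation. It is not proven: rounding the one-sided values to the nearest hundred gives the printed figure in only 18 of 30 cells, and the 10% baseline, ratio 1.2 cell (4,500 against 4,191) does not fit. Two-sided 85% power comes within 3%, or two units, in 12 of 30 cells, although it fits the ratio 1.1 column less well.
- A reader might infer that the study is underpowered. On the protocol's own count it is not. The loss scenarios are assumptions, and they apply to the smallest database at the most demanding cell. At 20% baseline the corrected requirement is 8,714, so even a 50% loss would leave enough (11,000).

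**Conclusion.** Table 2 is wrong as written. Its sizes do not deliver the stated 90% power at two-sided p<0.05 in 24 of 30 feasible cells; at a ratio of 1.1 the true power is 82% to 87%. Two further cells describe impossible compliance. These findings rest only on the inputs in section 9.5 and hold whatever the cause.

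The claim of at least 90% power at 10% baseline and ratio 1.1 still holds, at about 93%, under two assumptions: that Belgium supplies 22,000 eligible prescriptions in each period, and that these are independent. Neither is established. The 22,000 is a 2015 count, no pre-period count is given, and one patient may contribute several prescriptions. The margin is about 11%, not 38%, so a loss of more than about 10% (1 − 19,747/22,000) would take this cell below 90%.

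This is a real error in a stated figure that should be corrected. It changes no data collection or analysis, so it is not a critical flaw.

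**What to change.** Replace Table 2 with values for the stated two-sided test:

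| Baseline | 1.1 | 1.2 | 1.3 | 1.4 |
|---|---|---|---|---|
| 10% | 19,747 | 5,142 | 2,375 | 1,385 |
| 20% | 8,714 | 2,252 | 1,032 | 597 |
| 30% | 5,037 | 1,289 | 585 | 335 |
| 40% | 3,198 | 807 | 361 | 203 |
| 50% | 2,095 | 519 | 227 | 124 |
| 60% | 1,359 | 326 | 137 | 72 |
| 70% | 834 | 188 | 73 | 34 |
| 80% | 440 | 85 | not applicable | not applicable |

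If these are rounded, round up. Restate the conclusion as conditional: at 10% baseline and a ratio of 1.1, power is at least 90% provided that each period supplies about 19,750 eligible, independent prescriptions, and is about 93% at 22,000.

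Do not relabel the existing table as one-sided. The primary risk ratio is reported with a 95% confidence interval, which corresponds to a two-sided 5% test, and relabelling would separate the sizing from the planned inference.

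The cost is one table and one sentence, with a slightly less favourable statement of power.
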